12.6.2. Primary Safety Analyses

Main Analysis

The number and proportion of subjects experiencing device- and/or procedure-related serious adverse events will be tabulated for each study group. Non-inferiority through 36 months will be calculated using a normal approximation test (Z-test) for a difference in binomial proportion. Non-inferiority will be achieved if the lower limit of the 95% confidence interval for the difference in proportions (Comparator – Altis) is greater than -0.10 in the mITT analysis population. If non-inferiority is achieved and the lower limit of the 95% confidence interval for difference in proportions (Comparator – Altis) is greater than 0, superiority of Altis can also be claimed. As this follows a simple closed test procedure, no multiplicity adjustment is necessary.

The primary analysis of this endpoint will include all available data from the mITT analysis population. Subjects that have not experienced a device- and/or procedure-related serious event and who have missing data at 36 months will be assumed to be free of such an adverse event.

Sensitivity Analyses

The potential impact on the endpoint inference of all subjects with missing primary safety endpoint data will be assessed via various sensitivity analyses that include best case, worst case and tipping point analysis. In addition, a Kaplan-Meier product limit analysis that right censors subjects lost to follow-up will be conducted to further understand the potential impact of subject loss. All sensitivity analyses will be based on the mITT analysis set.

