10.2. Sample Size Estimation for Primary Safety Endpoint

The sample size for the primary safety endpoint was calculated to detect a non-inferiority limit of 10% assuming an underlying rate of device and procedure related serious adverse event of 10% in each group with 80% power. The rate of serious device and/or procedure related adverse events in the IDE study was 2.7% (3/113) through 12 months of follow-up. A conservative estimate of 10% was used for the purpose of sample size estimation to account for the additional follow-up time and to ensure adequate power. This resulted in total of 284 subjects required (142 subjects per group). As all subjects are accounted for in the final analysis (subjects with missing data will be assumed to be free of such an adverse event), no accounting for attrition is necessary.

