10.4. Level of Significance and Power

All tests of significance will be performed at the two-sided 0.05 significance level (one-sided 0.025), unless otherwise specified. As both the primary effectiveness and safety objectives must be met for study success, no adjustment for multiplicity is required. Additionally, the powered secondary safety endpoints for (1) device and/or procedure related adverse events, and (2) revision or resurgery will be tested hierarchically in the order presented in the event the primary safety objective is met. Therefore, no adjustment for multiplicity is required.

10. Data Structure and Handling

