12.1. General Considerations

All analyses will be performed by an independent statistician. Continuous variables will be summarized with means and standard deviations or as medians and interquartile ranges. Categorical variables will be summarized with the number and proportion of subjects in each category. Binary outcomes will be presented as proportions with corresponding 95% asymptotic confidence limits. Unless otherwise specified, two-sample t-test for independent groups or paired t-test will be used to test the means of continuous measures between groups, as appropriate. If assumptions of parametric tests are grossly violated, an equivalent non-parametric method may be sought. Fisher's exact test or binomial test will be employed to test categorical (including dichotomous) measures between groups.

The surgery date will be considered study day 0.

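### The two safety tests with a 10-point margin leave the interval method open; read as a Wald interval, they exceed the stated one-sided 2.5% error when event rates are low

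*SAP*

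**What the plan says.** SAP 12.6.2 (primary safety) and 12.7.2 (revision/resurgery) both use a "normal approximation test (Z-test) for a difference in binomial proportion". Non-inferiority is declared if the lower 95% limit for Comparator minus Altis "is greater than -0.10 in the mITT analysis population". SAP 7.2 and 7.4 state the matching hypotheses, and protocol 7.5 and 7.6.2 use the same test.

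The interval is described only in general terms, in SAP 12.1: "Binary outcomes will be presented as proportions with corresponding 95% asymptotic confidence limits". Nothing says whether the variance is pooled, unpooled or restricted to the null, and no score or exact method is named for these tests.

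The error claimed is in SAP 10.4: "All tests of significance will be performed at the two-sided 0.05 significance level (one-sided 0.025), unless otherwise specified".

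On event rates, SAP 10.2 sizes primary safety "assuming an underlying rate of device and procedure related serious adverse event of 10% in each group with 80% power" and describes that 10% as conservative. It also reports: "The rate of serious device and/or procedure related adverse events in the IDE study was 2.7% (3/113) through 12 months of follow-up". SAP 10.3 expects revision/resurgery to be rarer than the primary safety event but gives no figure.

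**The concern.** The usual Wald limit estimates each arm's variance from its own observed proportion. At the edge of the null hypothesis, where the true Altis rate is 10 points above the comparator rate, samples in which Altis happens to have few events also produce a small estimated variance. The interval is then too narrow just when the observed difference looks favourable. The effect grows as rates approach zero, and its direction is to pass Altis too often.

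Primary safety is one of two objectives that must both be met for study success, and passing it also opens the hierarchical secondary safety tests. Several features of the plan point to rates below 10%: the planning rate is called conservative, revision/resurgery is expected to be rarer, and subjects with no event and missing 36-month data are counted as event-free, which lowers the analysed rates further.

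**Working it through.** **Inputs.** Margin 0.10 (SAP 7.2, 7.4, 12.6.2, 12.7.2); one-sided 0.025, z = 1.960 (SAP 10.4); 178 per arm (SAP section 8, Trial Design); 142 per arm, the stated requirement for primary safety (SAP 10.2); planning rate 10% in each group; IDE rate 3/113 = 2.7% at 12 months.

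**Reproducing the plan's figure.** n = (1.960 + 0.842)² × 2 × 0.10 × 0.90 / 0.10² = 141.3, so 142 per arm, as in SAP 10.2. Dividing by 0.80 gives 177.5, so 178, as in protocol 7.9.3. With equal planning rates and equal arms, pooled and unpooled variances coincide, so the sample size does not reveal which one the test will use.

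**Exact error.** Let the comparator count be binomial (n, p) and the Altis count binomial (n, p + 0.10), the edge of the null. Sum the probabilities of all pairs of counts for which non-inferiority is declared.

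- Wald: declare if d − 1.960 × √[pC(1−pC)/n + pA(1−pA)/n] > −0.10, where d = pC − pA are observed values.
- Score (Farrington-Manning): declare if (d + 0.10)/SE₀ > 1.960, where SE₀ uses the maximum-likelihood rates constrained to differ by exactly 0.10.

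| Comparator rate | Altis rate | Wald error, 178 per arm | Score error, 178 per arm |
|---|---|---|---|
| 1% | 11% | 3.95% | 2.09% |
| 2.7% | 12.7% | 3.48% | 2.32% |
| 5% | 15% | 3.04% | 2.38% |
| 7.8% | 17.8% | 2.82% | 2.35% |
| 10% | 20% | 2.71% | 2.39% |

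The 7.8% row assumes the IDE 12-month risk stays constant for three years: 1 − (1 − 3/113)³ = 0.0776. Using a pooled variance at 178 per arm gives the same Wald column to two decimals. At 142 per arm and a 2.7% comparator rate the errors are 3.56% (Wald) and 2.09% (score); at 142 and 10%, Wald gives 2.80%.

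**A trial in which the method decides.** Take 178 per arm with 5 comparator and 14 Altis subjects with events. Then d = 5/178 − 14/178 = −0.0506.

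- Wald: SE = √[(0.0281 × 0.9719 + 0.0787 × 0.9213)/178] = 0.0237; lower limit = −0.0506 − 1.960 × 0.0237 = −0.097. Passes.
- Score: constrained rates 0.0203 and 0.1203; SE₀ = 0.0266; z = (−0.0506 + 0.10)/0.0266 = 1.86. Fails.

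The largest Altis count that passes, at 178 per arm:

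| Comparator events | Wald | Score |
|---|---|---|
| 0 | 11 | 9 |
| 3 | 13 | 12 |
| 5 | 14 | 13 |
| 10 | 17 | 17 |
| 18 | 23 | 23 |

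**Secondary safety test, margin 0.15.** At comparator rates of 14% (IDE) and 20% (planning), the Wald error is 2.59% and 2.51% at 178 per arm, and 2.66% and 2.50% at 112 per arm.

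**Power with both true rates at 10%.**

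| Per arm | Wald | Score |
|---|---|---|
| 178 | 88.2% | 86.3% |
| 164 | 85.4% | 83.7% |
| 142 | 80.6% | 77.8% |

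**The case against.** The Z-test is conventional, prespecified, and the same in protocol and SAP. At the sponsor's own planning rate the excess is about 0.2 points at 178 per arm and 0.3 at 142, which few would act on. The two methods then accept the same Altis count (23 against 18 comparator events), and elsewhere in the table they differ by at most two subjects. If both true rates are 2.7% they disagree in about 0.09% of trials, and at 5% each in about 0.8%. All of this stands, and it limits the weight of the point.

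A reader might go further than the documents allow in four ways.

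- **That the true error is 3.5%.** This takes 2.7% as the comparator's 36-month rate. It is a 12-month rate in subjects implanted with Altis (protocol section 2), and the SAP plans on 10% to allow for longer follow-up. The figure also needs a true Altis rate of 12.7%.
- **That the SAP specifies an unpooled Wald test.** It does not. That is a reading of a Z-test with asymptotic limits. The reading matters little at 178 per arm, where pooling gives the same error, but at 164 per arm and 2.7% pooling gives 3.22% against 3.50%.
- **That all safety tests are affected.** The 0.15-margin test is not, and 2.7% is not the only observed rate in the documents: its IDE rate is 14%.
- **That zero events in both arms would break the decision.** The Wald interval would have zero width, which is awkward to report, but the score test would also declare non-inferiority.

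None of this supplies the missing method. The sponsor's description of 10% as conservative, and its expectation of fewer revisions, make the low-rate region plausible.

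**Conclusion.** The point holds as a modest, conditional one. Under a Wald reading and equal arms of 178, the two 0.10-margin tests have a one-sided error between 2.7% (comparator rate 10%) and about 4.0% (1%), against a stated 2.5%, always towards non-inferiority. Where in that range the trial falls depends on a 36-month comparator rate that the documents do not give. Unequal arms, possible in a non-randomised cohort, change the figures: 200 Altis and 156 comparator subjects give 3.0% at a 2.7% comparator rate. The point does not invalidate the safety comparison. It is a cheap improvement to a primary decision rule whose interval method is at present unstated.

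**What to change.** In SAP 7.2, 7.4, 12.6.2 and 12.7.2, replace the unspecified Z-test by a named score interval for the difference in proportions (Miettinen-Nurminen or Farrington-Manning), with the same margins and one-sided 0.025. The SAP states that it prevails over the protocol, so the SAP wording is enough; protocol 7.5 and 7.6.2 can be aligned at the next amendment. The 0.15-margin test in 12.7.1 does not need the change, although one method throughout would be tidier.

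The cost is a wording change and a little power. At 10% in both arms, power stays above 80% at 178 per arm (86.3%), but at the 142 per arm that SAP 10.2 gives as sufficient it drops to 77.8%. The 80% power statement for primary safety should therefore be tied to 178 per arm.

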7.6.2 Revision/Resurgery

The number and proportion of subjects experiencing revision and/or resurgery will be tabulated for each treatment group. Non-inferiority at 36 months will be calculated using a normal approximation test (Z-test) for a difference in binomial proportion with the following null and alternative hypotheses:

$$H_0: \pi_c - \pi_T \leq -0.10$$

$$H_A: \pi_c - \pi_T > -0.10$$

where π_c is the proportion of patients who have the revision/resurgery endpoint during follow-up in the control group and π_T is the proportion of patients who have the revision/resurgery endpoint during follow-up in the treatment group.

Handling of Missing Data

The primary analysis of this endpoint will include all available data from the ITT analysis population. Subjects that have not experienced a revision/resurgery and who have missing data at 36 months will be assumed to be free of such an event. However, the potential impact on the

endpoint inference of all such subjects will be assessed via various sensitivity analyses that includes best case, worst case and tipping point analysis. In addition, a Kaplan-Meier product limit analysis that right censors subjects lost to follow-up will be conducted to further understand the potential impact of subject loss.

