This SAP should be read in conjunction with the study protocol and electronic case report forms (eCRF). This version of the plan has been developed with respect to the Altis 522 protocol version 4.0, dated November 01, 2018. Any changes to the protocol or eCRFs may necessitate updates to the SAP. If differences exist between the protocol and the SAP, the SAP shall prevail.

3. Applicable Documents

Document Number	Document Title
Study ID SU020	A Post-Market Evaluation of the Altis Single Incision Sling System versus Transobturator or Retropubic Mesh Sling in the Treatment of Female Stress Urinary Incontinence (Altis 522 Study)

4. Software

All tables, listings and figures will be produced using SAS Version 9.4 (SAS Institute, Cary, NC.) or a later version of SAS. All output will be in Microsoft Word, Microsoft Excel or RTF format. Other reporting software (such as R) may be used for data analysis, summarizations or visualization of data as necessary.

5. Trial Objectives

The purpose of this postmarket study is to compare the safety and effectiveness of the Altis Single Incision Sling (SIS) to an FDA cleared transobturator and/or retropubic mesh sling through 36 months.

The primary safety and effectiveness objectives of this study are:

1. To demonstrate that the rate of device and/or procedure related serious adverse events associated with use of Altis SIS is non-inferior compared to the rate associated with use of transobturator and/or retropubic slings at 36 months.
2. To demonstrate that the rate of effectiveness associated with use of Altis SIS is non-inferior to the rate associated with use of transobturator or retropubic mesh slings for the treatment of stress urinary incontinence at 6 months.

The secondary objectives of this study are:

3. To demonstrate that the rate of device and/or procedure related adverse events defined as organ perforation, bleeding, mesh exposure in the vagina, mesh erosion into the bladder, pelvic pain, infection, de novo dyspareunia, urinary retention, recurrent incontinence, other urinary problems and neuromuscular problems associated with use of Altis SIS is non-inferior compared to the rate associated with use of transobturator and/or retropubic slings at 36 months.
4. To demonstrate that the rate of revision/resurgery associated with use of Altis SIS is non-inferior compared to the rate associated with use of transobturator and/or retropubic slings at 36 months.

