7.2. Primary Safety Hypotheses

The number and proportion of subjects experiencing device- and/or procedure-related serious adverse events will be tabulated for each study group. Non-inferiority at 36 months will be calculated using a normal approximation test (Z-test) for a difference in binomial proportion with the following null and alternative hypotheses:

$$H_0: \pi_C - \pi_T \leq -0.10$$

$$H_A: \pi_C - \pi_T > -0.10$$

where π_C is the proportion of subjects who have the primary safety endpoint during follow-up in the Comparator group and π_T is the proportion of subjects who have the primary safety endpoint during follow-up in the Altis group and 0.10 is the non-inferiority margin.

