7.4. Revision/Resurgery Hypotheses

The number and proportion of subjects experiencing revision and/or resurgery will be tabulated for each treatment group. Non-inferiority at 36 months will be calculated using a normal approximation test (Z-test) for a difference in binomial proportion with the following null and alternative hypotheses:

$$H_0: \pi_C - \pi_T \leq -0.10$$

$$H_A: \pi_C - \pi_T > -0.10$$

where π_C is the proportion of subjects who have the revision/resurgery endpoint during follow-up in the Comparator group and π_T is the proportion of subjects who have the revision/resurgery endpoint during follow-up in the Altis group and 0.10 is the non-inferiority margin.

7. Trial Success Criteria

The Altis 522 will be evaluated according to the primary effectiveness and safety objectives. The study will be considered a success if both primary objectives (effectiveness and safety) are met.

8. Trial Design

This is a prospective, post-market, multi-center, cohort assessment comparing Altis SIS (n=178) and transobturator and/or retropubic slings (n=178) in the treatment of stress urinary incontinence, at up to 40 U.S. and International sites. Subjects will be followed for a total of 36 months with scheduled visits at 6, 12, 18, 24 and 36 months.

The study population will consist of adult female subjects with stress urinary incontinence who are clinically indicated for surgical intervention with a mesh sling. All study candidates who provide written informed consent and meet all the inclusion criteria and none of the exclusion criteria will be included in the study. Subject enrollment will continue until the required sample size is successfully reached. No site may enroll more than 20% of subjects without prior approval from Coloplast Corp.

Schedule of Procedures:

Data Collection	Baseline	Procedure	6 Month	12 Month	18 Month	24 Month	36 Month	Un-scheduled ⁴
Informed Consent Obtained	X							
Inclusion/Exclusion Criteria Verified	X							
Pregnancy Test	X ¹							
Urinalysis	X ²							
Medical History	X							
Procedural Data		X						
Cystoscopy		X						
Post Void Residual Test	X ³		X	X	X	X	X	
Cough Stress Test	X ³		X	X	X	X	X	
24-Hour Pad Weight Test	X ³		X ⁵					
Medication Documentation	X	X	X	X	X	X	X	

Data Collection	Baseline	Procedure	6 Month	12 Month	18 Month	24 Month	36 Month	Un-scheduled ⁴
Patient Global Impression of Improvement (PGI-I)			X	X	X	X	X	
Surgical Satisfaction Questionnaire (SSQ-8)			X					

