12.6.3. Propensity Score Analysis

In addition to the analyses of the primary effectiveness and safety endpoints noted above, a propensity analysis will be conducted to address the effect of potential confounding variables on study conclusions. Risk factors that will be analyzed include, but are not limited to:

- Age
- Parity
- BMI
- Smoking status
- Diabetes
- Hysterectomy status
- History of Multiple Urinary Tract Infections

For this analysis, a logistic regression model will be used to calculate the probability of treatment assignment given the covariates listed above (i.e., the propensity score). The covariates will not be grouped, resulting in one propensity score for each subject. The propensity score will be used in an adjusted regression model for each primary endpoint. A logistic regression model will be used for the primary effectiveness and safety endpoints.

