12.8. Interim Analyses

No formal interim analyses for this study are planned. However, per regulatory requirement set forth by FDA, interim (or annual, as required) post-market surveillance reports will be submitted. These reports will include all the required elements (e.g., summary of subject population, study milestones/enrollment elements), and summary and interpretation of study results. For the progress reports, endpoint results will be summarized as appropriate (e.g., via counts and percentages), however, no statistical testing will be performed and no p-values will be provided until data collection for this endpoint has been concluded.

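### The three powered safety tests count women who leave without a recorded event as event-free to month 36, so their error rate depends on drop-out and event timing, and the planned Kaplan-Meier analysis cannot change the decision

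*SAP*

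**What the plan says.** The primary safety objective is that the related serious adverse event rate with Altis "is non-inferior compared to the rate associated with use of transobturator and/or retropubic slings at 36 months" (SAP section 5). The hypotheses in SAP 7.2 compare proportions, for example the "proportion of subjects who have the primary safety endpoint during follow-up in the Comparator group".

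The deciding analysis is a Z-test on crude proportions with a margin of 0.10 (SAP 12.6.2; Protocol 7.5). Women with no recorded event "who have missing data at 36 months will be assumed to be free of such an adverse event". The rule is repeated for any related adverse event, margin 0.15 (SAP 12.7.1; Protocol 7.6.1). It is repeated again for revision/resurgery, margin 0.10 (SAP 12.7.2; Protocol 7.6.2), where women without the event "who have missing data at 36 months will be assumed to be free of such an event".

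Best-case, worst-case and tipping-point analyses are listed as sensitivity analyses. In addition, "a Kaplan-Meier product limit analysis that right censors subjects lost to follow-up will be conducted". The success rule refers to none of them: "The study will be considered a success if both primary objectives (effectiveness and safety) are met" (SAP section 7, Trial Success Criteria). The two secondary safety tests open only if primary safety is met (SAP 10.4).

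Protocol 7.9.6 expects drop-out to be uniform over time and at most 20% by study end. Neither document gives drop-out by arm or the timing of events.

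**The concern.** An event recorded before a woman leaves is counted. If none was recorded, she stays in the denominator as a complete 36-month non-event, although part of that time was not observed. Both arms' risks are then understated, but the margin does not move.

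The observed Altis excess shrinks when the later risk hidden by drop-out is larger in the Altis arm than in control. At the margin, with equal drop-out and similar event timing, this always happens, because the Altis risk is the larger one. If Altis events come much earlier than control events, the error vanishes or reverses. Unequal drop-out can push it either way. The study is open-label and not randomised, so equal drop-out cannot be taken for granted.

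The stated one-sided 0.025 is therefore not what the deciding analysis delivers. At stake are the primary safety claim, the two secondary claims behind it, and the superiority claims that the SAP allows from the same intervals.

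**Working it through.** **The plan's own figures.** One-sided 0.025 and 80% power (SAP 9 and 10.4) give (1.960 + 0.842)² = 7.849.
- Primary safety, 10% in both arms, margin 0.10: 7.849 × 2 × 0.10 × 0.90 / 0.10² = 141.3, so 142 per arm (SAP 10.2). 142/0.8 = 177.5, so 178 (Protocol 7.9.3).
- Any related adverse event, 20% in both arms, margin 0.15: 7.849 × 2 × 0.20 × 0.80 / 0.15² = 111.6, so 112 per arm; 112/0.8 = 140 (Protocol 7.9.4).

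All four figures reproduce.

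**Observed risk under the event-free rule.** Let p be an arm's true 36-month risk, d its drop-out proportion (uniform over 36 months) and F(t) its cumulative risk.

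Observed risk = (1 − d)p + d × mean of F(t) over the drop-out times.

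With constant hazard, the mean of F is 1 − p/Λ, where Λ = −ln(1 − p).
- Control, p = 0.10: Λ = 0.1054, mean F = 0.0509. At d = 0.20, observed risk = 0.8 × 0.10 + 0.2 × 0.0509 = 0.0902.
- Altis, p = 0.20: Λ = 0.2231, mean F = 0.1037. At d = 0.20, observed risk = 0.8 × 0.20 + 0.2 × 0.1037 = 0.1807.

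A true excess of 10 points appears as 9.1 points.

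**Direction.** Observed excess = true excess − (d_T p_T g_T − d_C p_C g_C), where g is the mean share of an arm's events still to come at drop-out. With equal drop-out and late events spread evenly, g is half the late share. There is then no shrinkage when the Altis late share equals p_C/p_T times the control late share. That ratio is 1/2 at 10% vs 20% and 4/7 at 20% vs 35%.

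**False non-inferiority, primary safety.** Exact binomial enumeration of the Wald 95% limit, 178 per arm, true risks 10% (control) and 20% (Altis). Peri-operative share means the share of the 36-month risk that falls before any drop-out. Late events follow a constant hazard.

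| Drop-out Altis/control | Peri-operative share Altis/control | Observed excess (points) | False non-inferiority |
|---|---|---|---|
| none | any | 10.0 | 2.7% |
| 10/10% | 0/0% | 9.5 | 3.6% |
| 20/20% | 0/0% | 9.1 | 4.9% |
| 10/10% | 50/50% | 9.8 | 3.2% |
| 20/20% | 50/50% | 9.5 | 3.7% |
| 20/20% | 100/100% | 10.0 | 2.7% |
| 20/20% | 50/0% | 10.0 | 2.8% |
| 20/20% | 75/25% | 10.25 | 2.3% |
| 20/20% | 100/0% | 11.0 | 1.4% |
| 20/20% | 0/100% | 8.1 | 8.1% |
| 25/15% | 0/0% | 8.3 | 7.3% |
| 15/25% | 0/0% | 9.8 | 3.2% |
| 30/10% | 0/0% | 7.6 | 10.5% |
| 10/30% | 0/0% | 10.5 | 2.0% |

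**Kaplan-Meier instead.** The 36-month risk difference with Greenwood variance, at least 20,000 simulated trials per scenario, gives 2.6% to 3.0% in every such scenario simulated, with drop-out unrelated to risk.

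**The two secondary endpoints**, constant hazard, equal drop-out of 0, 10 and 20%:
- Any related adverse event (20% vs 35%): 2.5%, 3.5%, 4.8%. Opposite timings at 20% drop-out give 0.9% (Altis early) and 10.5% (Altis late). Kaplan-Meier: 2.4% to 2.7%.
- Revision/resurgery (assumed 5% vs 15%, because the documents give no rate): 3.0%, 4.3%, 6.1%. Kaplan-Meier: about 3%.

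**Propensity model.** SAP 12.6.3 says "A logistic regression model will be used for the primary effectiveness and safety endpoints". A binary model carries the same coding. The true odds ratio at 10% vs 20% is 0.25/0.111 = 2.25. From the observed risks, unadjusted, it becomes 2.23 with equal 20% drop-out (9.0%, 18.1%). It becomes 1.96 with 30% Altis/10% control (9.5%, 17.1%) and 2.52 with the reverse (8.5%, 19.0%).

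**The case against.** The rule is disclosed, and the plan already commits to worst-case, tipping-point and Kaplan-Meier analyses that would expose a fragile conclusion. Sensitivity analyses do not normally decide. The endpoint is worded as observed events and the hypotheses refer to events during follow-up, which fits a crude proportion. The only drop-out figure is a uniform ceiling with no difference between arms, and Protocol 3.7 and 3.8 set out follow-up and retention measures. The largest error rates need scenarios that no text supports. Kaplan-Meier rests on an untestable assumption of its own, and changing the deciding analysis in an open-label study may not be blind to results.

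Much of this stands. The range tied to the protocol's drop-out figure is 2.7% to 4.9% for primary safety when both arms share the same event timing. The higher and lower values are assumptions. Kaplan-Meier is not exact under informative drop-out. With 20% drop-out per arm and constant hazard, primary safety error is:

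| Leavers' hazard | Event-free rule | Kaplan-Meier |
|---|---|---|
| Doubled, both arms | 6.3% | 3.8% |
| Doubled, Altis only | 8.4% | 5.4% |
| Doubled, control only | 3.6% | 1.9% |
| Halved, both arms | 4.0% | 2.1% |

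Kaplan-Meier is nearer 2.5% in all four. On the second safety endpoint it is nearer in three of four; the exception is control only (1.3%, against 2.8% for the event-free rule).

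The objection does not rescue the deciding rule. The objective is the 36-month rate, and the SAP itself says that event-free status is assumed. Disclosure does not control the error of the test on which success depends.

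**Conclusion.** The concern holds for all three powered safety endpoints. At the protocol's 20% uniform drop-out with constant hazard in both arms, the primary safety test's false non-inferiority rate is 4.9%. The nominal rate is 2.5%, and the same test gives 2.7% with complete follow-up. The direction is not fixed: assumed differences between arms in timing or drop-out give 1.4% to 10.5%, and there is no inflation if all events are peri-operative. These figures rest on true risks at the margin, 178 per arm and, except where stated, drop-out unrelated to event risk. Apart from the 20% uniform ceiling, every drop-out pattern and event timing is an assumption. This should be fixed before the 36-month comparison. It is not fatal, because the better analysis is already planned.

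**What to change.** - In SAP 12.6.2, 12.7.1 and 12.7.2 and Protocol 7.5 and 7.6, make the Kaplan-Meier 36-month risk difference (Greenwood variance, same margins) the deciding analysis.
- Censor at the last adverse event assessment. Count women who complete the 36-month visit as followed to month 36, because its window opens at day 1053. Name the read-out day and say how deaths without an event are treated.
- State that the method assumes non-informative censoring. Keep the event-free, best-case, worst-case and tipping-point analyses as sensitivity analyses, and report drop-out by arm and reason.
- In SAP 12.6.3 and Protocol 7.8, either state that the propensity-adjusted safety model keeps the event-free coding and is supportive only, or weight it for censoring.
- In SAP 10.2, replace the statement that attrition needs no allowance with the protocol's 20% allowance. The target of 178 per arm already includes it.

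**Cost.** A SAP and protocol amendment, with ethics and regulatory approval where applicable (Protocol section 11), dated before 36-month safety results are compared by arm. The study is open-label, and in progress reports "endpoint results will be summarized as appropriate (e.g., via counts and percentages"); whether this is by arm is not stated. The amendment should say whether safety counts by arm have already been seen. No new patients or data are needed. At 20% drop-out and equal true risks, power falls from 91% to about 84% (primary), from 96% to 92% (any related adverse event) and from 99% to 98% (revision/resurgery, assumed 5%). All stay above 80%.
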